7.1 Inclusion Criterion

- 1.) People with MS:
- Diagnosis of MS
- Received neuropsychological screening and mild cognitive problems identified (in WP2i IRAS ID: 276570)
- 2.) Related informants:
- Relative, friend or carer supporting a person with MS

3.) Clinicians:

- Health professionals (e.g., neurologists, MS nurse specialists, psychologists, occupational therapists) delivering the NEuRoMS screening and management pathway to people with MS.
- 4.) Intervention providers:
- Assistant psychologists or Research Nurses delivering the intervention to people with MS identified above in 1.)

All individuals: Aged 18 years or above, able and willing to give informed consent and able to communicate in English.

7.2 Exclusion Criteria

- •Do not have mental capacity to consent to take part in the study
- •Are unable to communicate in English (standardised materials are to be used which have not yet been developed for other groups)

7.3 Expected Participant Duration

NEuRoMS intervention = up to 4hours across up-to 6 sessions, these can be delivered completely remotely over telephone or video conferencing. Hybrid models will also be available (dependent on government and NHS advice) with approximately 1-2 sessions delivered face-to-face in clinic and 3-6 delivered over telephone or video conferencing (see Figure 2).

[figure not shown]
[figure not shown]

Figure 2. Qualitative study schedule for patient participants

7.4 Informed Consent

All participants will provide informed consent before they enter the study. Details of the study will be provided in a Participant Information Sheet, ensuring that the individual has sufficient time to consider participating or not (at least 24 hours).

[figure not shown]
Ten patients with mild cognitive problems will be invited to take part in a case study where they will receive the NEuRoMS intervention and complete a digitally-recorded interview (along with related informants, clinicians and intervention providers). A member of the clinical team will explain the study to the participant and confirm their contact details. With the patient's consent, these will be passed onto the intervention provider who will contact patients with Participant Information Sheet and Consent Forms. After allowing at least 24hours, the intervention provider will contact patients again to check if they wish to participate and will arrange their initial appointment. Patient participants will be asked to provide consent via Phone/Videoconferencing, Online via email or using a secure web application, or Post (see below) ahead of their initial NEuRoMS intervention session, or can bring their signed copies of their Consent Form along to the session (if meeting face-to-face — dependent on current Government and NHS COVID guidelines). During this session participants will also be provided with a cover letter, Participant Information Sheet and Consent Form for their related informants. Patients will be reminded to pass the study documents on to their related informants during the intervention sessions.

We will not inform GPs of patients' involvement in the study, as the care for the patients is provided by the MS Services once they are diagnosed with MS. A record of the patient's involvement in this study will be held in their medical notes at the MS clinic.

Clinicians and intervention providers will be informed of the study during the Site Activation Visit and provided with a Participant Information Sheet and Consent Form from a member of the research team. For more information see Section 6.4 on Participant Recruitment.

Telephone and email contact details for the research team will be provided for related informants, intervention providers and clinicians to ask questions and arrange an interview appointment where consent will be taken. To facilitate the consent process, informed consent will be obtained through the following routes, based on participant preference.

- 1. Phone or Videoconferencing: Participants will be offered the opportunity to provide their consent orally, over the telephone or videoconferencing. With the participant's approval, the consent process will be digitally recorded using an audio recorder. We will also record the date and time when oral consent was obtained using a researcher record of oral consent document to obtained participant consent. Participants will receive a hard copy of the researcher record of oral consent document for their own records, we will send this later by post.
- 2. Post: Participants can sign the Consent Forms and return these to us using a pre-paid envelope provided.
- 3. Online: Participants can sign the Consent Forms electronically via email or using a secure web application. An electronic copy of the signed Consent Form can be downloaded from the webpage.

Should there be any subsequent amendment to the final protocol, which might affect participation in the study, continuing consent will be obtained using an amended Consent Form which will be signed by the participant. If the Consent Form is amended during the study, the investigator shall follow all applicable regulatory requirements pertaining to approval of the amended Consent Form by the REC and use of the amended form (including for ongoing participants).

Participants will not be excluded from the study if they do not want to be audio recorded. A researcher record of oral consent and notes from the interview can be taken instead of an audio-recording should the participant prefer.

7.5 Participant Withdrawal

[figure not shown]
Participants may be withdrawn from the study either at their own request or at the discretion of the Chief Investigator or treating clinician (in the case of patient participants). Patient participants will be informed that this will not affect their future medical care. Participants will be made aware (via the information sheet and Consent Form) that should they withdraw all personal data will be destroyed but other data collected up to the point of withdrawal may still be used in the final analysis. All participants will be informed that if they withdraw their legal rights will not be affected.

If consent is withdrawn, the participants will be discontinued from the study. Due to the characteristics of the some members of the sample (i.e. having multiple sclerosis or being an informal carer), should any participant become tired or demonstrate that the interview session is causing them any discomfort or distress, we will check with them whether they wish to continue, and proceed only with their permission. Breaks will be provided where this is needed or requested.

8 Research Data

8.1 Data Analysis

Research data will consist of audio recordings of (i) interviews and (ii) NEuRoMS intervention sessions. Interviews will be audio-recorded and transcribed verbatim, with field notes made to capture contextual information, and analysed (on NVivo) using framework analysis. This is a hierarchical, matrix-based method developed for applied qualitative research (Pope, Ziebland, & Mays, 2000) (Ritchie & Lewis, 2003). Taking this type of analytical approach is appropriate for the purposes of the research, as framework analysis is particularly suited to research where the objectives of the study are clearly defined at the onset (i.e., to further develop and refine initial programme theory). The interview data will be mapped to thematic matrices (see Appendices for Logic Model) which reflect resources required for NEuRoMS to be delivered, contextual factors which influence its delivery, those mechanism which influence its affect and those outcomes which are described by interviewees. This will enhance our understanding of the key issues for people with MS and other stakeholders in relation to screening and intervention. It will allow us to explore the behavioural elements of the intervention, essential resources needed for, and barriers to screening and intervention delivery. If required, the framework will be revised to include new concepts or themes introduced during the interviews. Once all the data are mapped onto the framework, tables will be used to summarise each main theme. Each

theme will be interpreted to inform the development of the proposed screening and management pathway for subsequent elements of the wider NEuRoMS programme grant.

The intervention audio-recordings and intervention record forms will be mapped onto the intervention manual to determine 'how much' of the manual was covered in each session, what was left out, what the patients found difficult to follow, etc. This will give us some indication of how the intervention should be refined.

The audio-recordings of the interviews, monthly teleconferences and intervention sessions and intervention record forms will be treated as confidential documents and held securely in accordance with regulations. Each participant will be assigned a unique participant identity code number by the research team, for use on study documents and the electronic database (see section 10.5 for Confidentiality and Data Protection).

8.2 Participant Sample Size

[figure not shown]
Sample sizes for the interviews are based on our previous experience and extant literature, which suggest these numbers will achieve 'theoretical sufficiency' to answer specific questions (Dey, 1999) and inform the ongoing development of NEuRoMS. Purposive sampling will be used for the interviews. We intend to complete ten detailed qualitative case studies conducted with people with MS, and their related informants (n=10, one per participant, representing all three sites). We will interview all the intervention providers (Research Nurses/ Assistant Psychologists) (one per site; n=3), and four clinicians from each of the three screened sites (n=12).

9 Adverse Events

The occurrence of an adverse event as a result of participation within this study is not expected, since the trial involves a NEuRoMS intervention and qualitative interview only. However, it is possible that talking about cognitive difficulties may sometimes create distress for people with MS or their related informants during the study. This distress will be dealt with during the course of the intervention and the intervention sessions will address this on a participant by participant basis. The intervention will be delivered by a trained Assistant Psychologist or Research Nurse who will receive monthly supervision. So overall the risk has been assessed as negligible. As a result no adverse events (or serious adverse events) will be reported for this study.

In the event of discomfort/distress during interviews, the following protocol will be in place:

- 1. Ensure sufficient time to be given for debriefing after the meeting.
- 2. Facilitators/interviewers to be actively looking for cues of distress/discomfort and check with participants whether they wish to continue, and proceed only with their permission.
- If the participant no longer wish to continue and consent is withdrawn, one of the researchers (who is a health professional) will accompany the participant out of the room to allow debrief and to provide support, as needed.

- 4. Contact information on appropriate referral sources will be provided should participants feel they need further information/support on cognitive problems.
- 5. If needed, participants to be advised to approach their GPs.
- Contact details of the research team will be provided in case of any enquiry about the research or to discuss the feelings of the distress caused by the interview/discussions later on.

10 Regulatory Aspects

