screening profile and individual needs, but will focus on: psychoeducation, internal and external compensatory strategies; environmental modifications; and the importance of dealing with low mood and fatigue. Ten people with mild cognitive problems (3-4 from each site) will receive the NEuRoMS intervention and later take part in a semi-structured interview as part of 10 case studies. Qualitative analysis of the case studies will be reported to understand participants' experiences and identify any barriers/ facilitators to delivery of the screening and management pathway. The others will receive the NEuRoMS intervention following their next clinic appointment, when the intervention will be more established at each site.

We are interested in those with 'mild' cognitive problems in study, because the feedback we received from participants who took part in our previous cognitive rehabilitation trial (CRAMMS (Lincoln et al., 2019)) was that they had too severe cognitive problems to actually benefit from the rehabilitation. Participants felt that had they received the rehabilitation earlier, when their cognitive problems were milder, they may have been able to benefit more.

Research focus

The present study will investigate what potential benefits and issues people with MS who undergo neuropsychological screening encounter, and tries to identify any barriers/ facilitators to delivery of the screening and management pathway. Ten patients who experienced the neuropsychological screening (IRAS ID: 276570) and were identified as having mild cognitive problems, will be offered a manualized NEuRoMS intervention led by an Assistant Psychologist or Research Nurse. After completing the intervention, semi-structured interviews will be conducted with participants and related informants (family or carers) and clinicians to understand their experiences of the screening and management pathway. These qualitative case studies will help refine the pathway and facilitate its implementation.

5 Study Objectives

[figure not shown]
Primary Objectives and Outcomes

- To improve understanding of how the NEuRoMS screening and management pathway is integrated within routine clinical practice.
- To improve understanding of how the NEuRoMs intervention programme is experienced by those who deliver and receive it.

Secondary Objectives

- Refine intervention resource book and staff training package.
- Develop fidelity tools for the definitive trial.

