6.2 Study Outline

This qualitative study (WP2ii) involves interviews with 10 patients (and related informants, clinicians and intervention providers) who experienced the screening and management pathway and are completing the NEuRoMS intervention.

A self-administered, brief online neuropsychological screening (completed at home prior to clinic visit) or tablet-based version (completed in clinic prior to routine appointment -dependent on Government and NHS advice) that can be administered with minimal support from clinical staff will be introduced as part of usual care at three NHS sites. The screen will capture cognitive function (memory, information processing and executive function), mood and fatigue. The screen will be used to facilitate discussions about managing cognitive problems between patients and clinicians.

The current study will recruit ten people with MS who received the screen and were identified as having mild cognitive problems. These participants will be offered the NEuRoMS intervention during a discussion of their screening results with a member of their clinical team (MS nurse, neurologist, OT, psychologist or physiotherapist). Patients will be selected using a maximum variation sampling technique (varied according to demographic and illness characteristics).

The newly designed NEuRoMS intervention is multi-faceted, involving various components (i.e., information provision, goal setting), and a range of strategies and techniques (e.g., psychoeducation, compensatory strategies, boosting cognitive reserve), delivered by a trained Research Nurse or Assistant Psychologist (under the supervision of a clinical psychologist). Sessions will predominately be delivered remotely via videoconferencing and telephone sessions, however those who prefer to undertake intervention sessions face-to-face can opt to do so for the first two sessions (dependent on Government and NHS advice). The Research Nurse or Assistant Psychologist will receive monthly supervision (60 minutes) via telephone/videoconference or face-to-face (depending on current government and NHS COVID guidelines) with a clinical psychologist.

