 - O Clear and understandable?
 - o Empathetic? Helpful?
- How do you think we could improve the cognitive management programme in the future?
- Have you experienced any changes since taking part in this study?
 - o What are these changes?
 - o How do you make sense of these changes?
- Is there anything else you would like to tell me about?

NEuRoMS WP2ii Qualitative Study: Clinician/ Intervention Provider-Participant Semistructured interview Guide

Final Version 1.0: 16.01.2020

[Note: As per the methodology, the semi-structured interview is only a guide, and is necessarily an iterative process (i.e., it gets modified slightly after each interview, based on the information that participants provide).]

Demographics

[figure not shown]
Gather demographic information about the participant and their job role.

Screening and management pathway

- How did the screening and management pathway work in your service?
- How well did the screening and management pathway work with your systems?
- What were the main facilitators to integrating the screening and management pathway within your service?
- What were the main barriers to integrating the screening and management pathway within your service?
 - O What can be done about the barriers?

NEuRoMS cognitive management programme (only for intervention providers)

- Please can you tell me about your experiences of delivering NEuRoMS cognitive management programme?
 - o What went well?
 - O What were the difficulties and how did you overcome them?
 - o How did you find the training that you received?
 - o How did you find using the manual?
 - o How did you find the clinical supervision at site/ by the trial therapists?
 - o How did you find the monitoring of your practice during the research study?
- How did participants find the NEuRoMS cognitive management programme?
 - Were there any particular aspects which were good or bad?
 - o Did participants experience any changes/benefits from the cognitive management programme?
- How do you think the cognitive management programme could be improved in the future?

NEuRoMS WP2ii Qualitative Study: Family Member/ Carer -Participant Semi-structured interview Guide

Final Version 1.0: 16.01.2020

[Note: As per the methodology, the semi-structured interview is only a guide, and is necessarily an iterative process (i.e., it gets modified slightly after each interview, based on the information that participants provide).]

Demographics

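### Section 9 foresees distress but rules out all adverse and serious adverse event reporting, with no recording step, so any harm information would be incidental and unsystematic

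*Protocol*

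**What the plan says.** Section 9 (Adverse Events) argues in four steps.

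- Adverse events from taking part are not expected, because the study consists of the intervention and an interview.
- A specific harm is nevertheless foreseen: "it is possible that talking about cognitive difficulties may sometimes create distress for people with MS or their related informants during the study".
- Distress is to be handled, not recorded. For the sessions: "This distress will be dealt with during the course of the intervention and the intervention sessions will address this on a participant by participant basis". For the interviews, a list of management steps follows the words "In the event of discomfort/distress during interviews, the following protocol will be in place".
- After noting that providers are trained and supervised monthly, the section says "So overall the risk has been assessed as negligible", and then "As a result no adverse events (or serious adverse events) will be reported for this study".

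The last sentence covers serious events and makes no exception for events related to a session or interview.

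On how new the intervention is, Section 6.2 says "The newly designed NEuRoMS intervention is multi-faceted, involving various components". Section 4 says of patients outside the ten case studies: "The others will receive the NEuRoMS intervention following their next clinic appointment, when the intervention will be more established at each site".

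Section 10.1 lets the sponsor and funder discontinue the study on safety grounds, taking advice from the Programme Steering Committee as appropriate. It also requires accidental protocol deviations to be documented and reported at once to the Chief Investigator and sponsor.

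**The concern.** The reasoning in Section 9 is circular. An opinion formed before the study, that the risk is negligible, justifies not reporting the events that would bear on that opinion. This is an explicit rule and not a detail left for a later document.

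Two things are at stake. The first is oversight. As written, a serious event related to a session has no stated route to the sponsor, whereas an accidental protocol deviation does. The right to stop for safety then rests on no event reporting. The second is information. This stage is meant to refine a new intervention before a definitive trial, and it would end without a count of even the one harm that the protocol predicts.

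**Working it through.** The protocol gives no adverse event rate and no power-based sample size, so there is no figure of its own to reproduce. The check compares the text and then asks how much 10 patients could show.

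**Step 1: is there a recording step anywhere?**

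| Place | What it provides | Records or reports harm as such? |
|---|---|---|
| Section 9, sessions | Distress handled case by case | No step stated |
| Section 9, interviews | Watching for cues, permission checks, debrief, referral contacts | No step stated |
| Section 6.2 | Session audio, case notes, record forms | Kept for fidelity checks and supervision |
| Section 8.1 | Recordings and record forms mapped to the manual; interviews analysed by framework | Harm could appear as a theme, but is not counted |
| Section 10.5 | Confidentiality may be broken if someone discloses a risk to self or others | A disclosure exception, not a harm record |
| Section 15, interview guides | Questions on unhelpful aspects and on changes | Open prompts, not systematic |
| Section 10.1 | Right to stop for safety | No event reporting feeds it |

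Harm can come to light by several routes. None of them is stated to record it systematically, and Section 9 bars reporting it as an adverse event.

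**Step 2: how many contacts does the rule cover?** Inputs: 10 patients and 10 informants (Section 8.2); up to 6 sessions per patient (Section 6.3).

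- Sessions, at most: 10 × 6 = 60.
- Patient and informant interviews: 10 + 10 = 20.
- Total, at most: 60 + 20 = 80. This is a ceiling, since six is the maximum number of sessions.

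**Step 3: what could recording reveal?** Let *p* be the true proportion of patients who have a given type of event. The values of *p* are assumptions, and patients are treated as independent. P(at least one event) = 1 − (1 − p)^10.

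| Assumed p | Calculation | Chance of at least one event |
|---|---|---|
| 1% | 1 − 0.99^10 | 9.6% |
| 5% | 1 − 0.95^10 | 40.1% |
| 10% | 1 − 0.90^10 | 65.1% |
| 20% | 1 − 0.80^10 | 89.3% |
| 30% | 1 − 0.70^10 | 97.2% |

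**Step 4: what could recording not show?** If no events occur in 10 patients, the exact one-sided 95% upper bound solves (1 − p)^10 = 0.05, so p = 1 − 0.05^(1/10) = 0.259, or about 26%. A clean record would not establish negligible risk.

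Recording would probably expose a common harm. It would usually miss a rare one and could not exclude one.

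**The case against.** The case on the other side is substantial, and much of it stands.

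- **Harm information is not shut out.** A reader might infer from Section 9 that the study can yield none. The documents do not support that: the routes in Step 1, and the monthly clinic teleconferences used as data (Section 6.2), can all bring up bad experiences.
- **The guides are not one-sided.** The provider question "Did participants experience any changes/benefits from the cognitive management programme" might suggest that only good news is sought. The same guide also asks about good or bad aspects and about difficulties, and the patient and informant guides ask what was unhelpful and put a neutral question about changes.
- **Distress is not ignored.** Section 9 sets out how it is to be handled. The gap is in recording and escalation.
- **Mood problems are not overlooked.** Sections 7.1 and 7.2 do not exclude patients with moderate to severe mood problems, but Section 4 routes them to referral under routine care.
- **First use is an inference.** The text says only that the intervention is newly designed and not yet established at the sites. Nor does it say that the definitive trial will adopt Section 9's risk statement.
- **The study is small and qualitative.** Estimating harm is not an objective, and the rule invalidates neither primary objective.

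Two further replies are weaker. The ban on reporting could mean onward reporting only, but no recording step is stated either. The sponsor's procedures, which Section 10.9 says govern conduct, might contain a reporting route. They are not in the documents, and an explicit statement that nothing will be reported would conflict with them.

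**Conclusion.** The concern holds in a limited form. Section 9 predicts distress, calls the risk negligible in advance, rules out all adverse and serious adverse event reporting on that basis, and states no step to record distress. Harm information on a newly designed intervention would therefore be incidental and unsystematic, and no event reporting would support the right to stop for safety in Section 10.1.

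The statistical value of recording is modest, and the event rates behind it are assumptions. It offers a good chance of seeing a common harm, but no ability to confirm negligible risk. A reader might take the missing data to be what prevents that confirmation; the number of patients would prevent it in any case. The stronger reason for change is that a serious related event should have a stated reporting route.

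Severity is moderate. The primary findings on integration and experience are not undermined.

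**What to change.** Replace the closing sentence of Section 9's risk paragraph with a rule to this effect:

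- Distress episodes, and adverse events judged related to an intervention session or interview, are logged with date, contact, relatedness and outcome. The existing intervention record form serves for sessions and the interview field note for interviews.
- Serious related events are reported to the sponsor.
- Counts are given descriptively with the results, with no claim that a low count establishes safety.

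The new text should name who judges relatedness. Sections 9 and 10.1 should be reconciled so that the right to stop for safety has a stated source of information.

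Optionally, reword the provider question to ask about changes, good or bad. The patient and informant guides already have neutral prompts and need no edit.

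The cost is one field on the form, a matching entry in the field note, one paragraph in the protocol, a small recording burden for providers and interviewers, and an amendment, with ethics committee review under Section 10.1 where required. No extra visits or procedures are needed.
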